Study Design: This is an open-label, Phase 1b dose-escalation and Phase 2 expansion study evaluating the safety, efficacy, tolerability, and pharmacokinetics of GS-9973 in combination with VCR and dexamethasone.

There will be four dose levels in the dose escalation phase where cohorts of 3 to 6 subjects will sequentially enroll into one of the dose levels using a 3+3 dose escalation design. The starting dose level for the first cohort is defined as Dose Level 1.

Dose Level	GS-9973	Vincristine (VCR)
1	200 mg BID	0.5 mg per dose
2	400 mg BID	0.5 mg per dose
3	400 mg BID	1 mg per dose
4	400 mg BID	2 mg per dose

Dose Escalation: Induction (Lead-in, Cycle 1 and Cycle 2)

Lead-in (GS-9973 Monotherapy): Beginning on Day -7 of Lead-in, GS-9973 will be administered orally twice daily (BID) for 7 days as a single agent.

Cycle 1 and Cycle 2 (GS-9973, VCR, dexamethasone, CNS Prophylaxis):

GS-9973 will be continuously administered orally BID in combination with chemotherapy for the duration of the study treatment.

VCR will be administered on Days 1, 8, 15 and 22 of each 28-day cycle for Cycle 1 and Cycle 2 only.

Dexamethasone (20 mg twice daily for 4 days) will be administered orally during Cycle 1 on Days 8-11 and Days 22-25 and during Cycle 2 on Days 1-4 and Days 15-18.

[figure not shown]
CNS prophylaxis per institutional standard will be given on Day 28 (\pm 3 days) of Cycle 1 and Cycle 2.

Bone marrow (BM) aspirate/biopsy will be performed during screening (within 28 days prior to the start of study treatment), Cycle 1 on Day 8 and during both Cycle 1 and Cycle 2 on Day 28.

Imaging (computerized tomography [CT] with contrast or Positron Emission Tomography (PET) scan should be performed for subjects with extramedullary disease (EMD) if these are the only sites of evaluable disease (no BM involvement) to evaluate disease status and response, at screening, Cycle 1 Day 8 and Day 28, and Cycle 2 Day 28. Imaging will be evaluated using the NCCN guidelines version 2.2016 (Patients with no BM involvement and only EMD will not require BM aspirate/biopsy on cycle 1 day 8 and day 28, and cycle 2 day 28).

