Appendix 4. Response assessment in ALL

Assessment of clinical response will be made according to NCCN guidelines on ALL Version 2. 2016 with the exception of Partial Remission, Overall Response Rate, Refractory Disease, and Relapsed Disease. The major criteria for judging response will include physical examination and examination of blood and bone marrow. All laboratory studies that are abnormal prior to study will be repeated to document the degree of maximal response.

Response criteria for blood and bone marrow

Complete Remission (CR)

CR requires all of the following:

- No circulating blasts or extramedullary disease (no lymphadenopathy, splenomegaly, skin/gum infiltration/testicular mass/CNS involvement
- Trilineage hematopoiesis (TLH) and < 5% blasts in bone marrow aspirate.
- Absolute Neutrophil Count (ANC) > 1,000/uL.
- Platelets > 100,000/uL.

CR with incomplete blood count recovery (CRi)

CRi meets all criteria for CR except platelet count and/or ANC:

• Platelets $\leq 100, 000/ \text{ uL}$ and/or ANC is $\leq 1,000/\text{uL}$

Overall response rate (ORR=CR+CRi+PR)

Partial Remission (PR)

Note: PR is not defined per NCCN guidelines but defined in this protocol. PR requires all of the following: Meets all criteria for CR except for BM blasts:

• bone marrow may contain \geq 5% but less than 25% blast morphology

Refractory disease: Failure to achieve CR, CRi or PR at the end of induction

Progressive disease (PD): increase of at least 25% in the absolute number of circulating or bone marrow blasts or development of extramedullary disease

Relapsed disease: reappearance of blasts in the blood or bone marrow (> 5%) or in any extramedullary site after a CR / CRi/PR.

Response criteria for mediastinal/extramedullary disease:

CR: Complete resolution of mediastinal enlargement or extramedullary mass/es by CT. For patients with a previous positive PET scan, a post-treatment residual mass of any size is considered as CRE as long as it is PET negative.

PR: > 50% decrease in the SPD of the mediastinal enlargement or extramedullary mass/es from baseline. For patients with a previous positive PET scan, post-treatment PET must be positive in at least one previously involved site.

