PD: > 25% increase in the SPD of the mediastinal enlargement or extramedullary mass/es from nadir or development new mediastinal/extramedullary mass/es. For patients with a previous positive PET scan, post-treatment PET must be positive in at least one previously involved site.

No Response (NR): failure to quantify for CR, PR or PD

Relapse: Recurrence of mediastinal enlargement after achieving CR. For patients with a previous positive PET scan, post-treatment PET must be positive in at least one previously involved site.

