Appendix 7.NCCN Guidelines (version 2.2016)

Response assessment

Response Criteria for Blood and Bone Marrow:

- Complete Response (CR):
 - No circulating blasts or extramedullary disease
 - No Lymphadenopathy, splenomegaly, skin/gum infiltration/testicular mass/CNS involvement
 - ➤ Trilineage hematopoiesis (TLH) and <5% blasts
 - ➤ Absolute neutrophil count (ANC) >1000/microL
 - Platelets >100,000/micro/L
 - ➢ No recurrence for 4 weeks
- Complete Response with incomplete blood count recovery (CRi):
 Meets all criteria for CR except platelet count and/or ANC
- Overall response rate (ORR = CR + CRi)
- Refractory disease
 - ➢ Failure to achieve CR at the end of induction
- Progressive disease (PD)
 - Increase of at least 25% in the absolute number of circulating or bone marrow blasts or development of extramedullary disease
- Relapsed disease
 - Reappearance of blasts in the blood or bone marrow (>5%) or in any extramedullary site after a CR

Response Criteria for Mediastinal Disease

- CT of chest with IV contrast and PET imaging should be performed to assess response
- CR: Complete resolution of mediastinal enlargement by CT. For patients with a previous positive PET scan, a post-treatment residual mass of any size is considered a CR as long as it is PET negative
- PR: >50% decrease in the sum of the product of the greatest perpendicular diameters (SPD) of the mediastinal enlargement. For patients with a previous positive PET scan, post-treatment PET must be positive in at least one previously involved site
- PD: >25% increase in the SPD of the mediastinal enlargement. For patients with a previous positive PET scan, post-treatment PET must be positive in at least one previously involved site
- No Response (NR): failure to qualify for PR or PD
- Relapse: recurrence of mediastinal enlargement after achieving CR. For patients with a previous positive PET scan, post-treatment PET must be positive in at least one previously involved site

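### In Appendix 4, extramedullary PD can miss a new mass after an earlier positive PET, and one scan can meet both PR and PD with no order stated

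*Protocol*

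**What the plan says.** Protocol Appendix 4 has two response lists, one for blood and marrow and one for mediastinal or extramedullary disease (EMD).

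In the EMD list:
- **PD:** "PD: > 25% increase in the SPD of the mediastinal enlargement or extramedullary mass/es from nadir or development new mediastinal/extramedullary mass/es".
- **PR:** "PR: > 50% decrease in the SPD of the mediastinal enlargement or extramedullary mass/es from baseline".
- **PET condition, attached in the same words to PR and PD:** "For patients with a previous positive PET scan, post-treatment PET must be positive in at least one previously involved site".
- **CR:** complete resolution on CT or, after an earlier positive PET, "a post-treatment residual mass of any size is considered as CRE as long as it is PET negative". I read the undefined CRE as CR, as in Appendix 7.
- **NR:** "No Response (NR): failure to quantify for CR, PR or PD".

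The blood and marrow list counts as PD an "increase of at least 25% in the absolute number of circulating or bone marrow blasts or development of extramedullary disease". It has no PET condition, and its CR requires that no extramedullary disease be present.

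Appendix 7 reproduces the NCCN criteria. Its mediastinal rule is "PD: >25% increase in the SPD of the mediastinal enlargement", with the same PET sentence but no nadir and no new masses. The opening of Appendix 4 lists its departures from NCCN (partial remission, overall response rate, refractory and relapsed disease). PD is not among them.

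SAP Section 6 refers only to NCCN version 2.2016 and to investigator assessment. SAP Section 6.2.1 drops the pointer to Appendix 4 that Protocol Section 8.1.3 gives for marrow PR. Neither document ranks the categories.

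**The concern.** A condition that asks for activity at an old site fits a PD rule about growth of that site. It does not fit a rule that also covers new masses, because a new mass is by definition not at an old site. Appendix 4 widened the rule and kept the condition.

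The second difficulty is the reference points. PR looks back to baseline and PD to the lowest value, and extramedullary PR does not require that no new mass has appeared. A tumour that shrank and then regrew can satisfy both.

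Subjects with EMD only are eligible (Protocol Section 4.2, criterion 2c) and need no on-study marrow, so their classification leans heavily on the imaging list. Therapeutic response is a secondary objective. At stake is whether someone who is progressing at the end-of-induction scan can be counted in the overall response rate.

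**Working it through.** **1. Denominators.** Protocol Section 8.9 plans 3 + 3 + 6 + 6 = 18 evaluable subjects with 10% unevaluable: 18 / 0.90 = 20. The plan's figure is reproduced. It is not in dispute and serves here only to size the effect.

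**2. New PET-positive mass.** Take baseline SPD 100 and current SPD 30, and apply the EMD list literally. Appendix 4 does not say whether a new mass enters the SPD; I assume the total stays below 50.

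| Earlier PET | Old sites now | EMD-list PD | EMD-list PR | General PD line |
|---|---|---|---|---|
| Positive | PET-negative | No (PET condition fails) | No (same condition fails) | Yes |
| Positive | At least one PET-positive | Yes | Yes | Yes |
| Never positive | Condition does not apply | Yes | Yes | Yes |

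In the first row the two lists in one appendix disagree. The new mass is neither resolved nor a PET-negative residual, so CR fails on a natural reading and the subject falls to NR. In the other two rows PR and PD are met together.

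**3. Regrowth from nadir.** Let B be baseline, N nadir and S the current SPD.
- PR by size: S < 0.5 B.
- PD by size: S > 1.25 N.
- Both: 1.25 N < S < 0.5 B, which is possible only if N < 0.5 B / 1.25 = 0.4 B.

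With B = 100:

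| Nadir | S values meeting both |
|---|---|
| 20 | 25 to 50 |
| 30 | 37.5 to 50 |
| 39 | 48.75 to 50 |
| 40 or more | none |

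Example: 100 at screening, 20 at Cycle 1 Day 28, 30 at Cycle 2 Day 28. From baseline (30 − 100)/100 = −70%, which is PR. From nadir (30 − 20)/20 = +50%, which is PD. The PET sentence is the same for both, so it cannot separate them, and NR applies only when all three categories fail.

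**4. Can it arise?** The Protocol Synopsis schedules imaging "at screening, Cycle 1 Day 8 and Day 28, and Cycle 2 Day 28". Two on-treatment scans precede the end-of-induction scan, so a nadir can fall before it.

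**5. Size for one subject.** 1/20 = 5.0 points overall (1/18 = 5.6), 1/6 = 16.7 points at a six-subject level and 1/3 = 33.3 points at a three-subject level. For scale, the exact 95% interval for 1 of 20 is 0.1% to 24.9%, against 0% to 16.8% for 0 of 20.

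**The case against.** **The CR inference.** A reader might infer that a progressing subject is scored CR, because the residual-mass sentence accepts any size if PET-negative. That follows only if the sentence is read in isolation. A new PET-positive mass is an unresolved extramedullary mass and not a PET-negative residual, and the blood and marrow list would refuse CR and call PD. On the natural reading PD becomes NR, and NR enters no response numerator. This objection stands; what it leaves is a contradiction between the lists.

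**Scope of the new-mass gap.** It exists only after an earlier positive PET. For everyone else a new mass is PD. This stands too.

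**The PR rate.** PR is counted as a best response. In the nadir case N < 0.4 B, so the earlier scan already met the PR size rule and the PR rate may not change. This stands for that rate. The overall response definition has no such wording and is tied to the end of induction, so the overlap still matters there.

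**Other evidence.** Blood counts and physical examination also inform response, and the investigator makes the call. True, but neither supplies an order between PR and PD on the same scan.

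**Materiality.** The endpoints are descriptive, expansion was cancelled for low response, and only a synoptic report is planned. SAP Section 6.2.2 lists response and EMD assessments by subject, so a case would be visible. This limits the importance but does not tell anyone how to score the case.

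**Conclusion.** The point holds in limited form. First, after an earlier positive PET with old sites now PET-negative, a new PET-positive mass is PD under the general line but not under the imaging list. Second, extramedullary PR and PD can both be met on one scan, through regrowth from a nadir below 40% of baseline or through a new mass while PR is still met, and no precedence is stated. The second defect is the one that can place a progressing EMD-only subject in the overall response numerator at end of induction.

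The documents permit that scoring but do not require it. Nor do they show that any rate is actually biased: the number of EMD-only subjects is not given and could be zero, so the point shifts above are per-subject arithmetic. The primary safety endpoint, dose-limiting toxicity rules, escalation table and sample size are unaffected. The conclusion rests on a literal reading of the EMD list and on Appendix 4 governing. Since PD is missing from its stated exceptions to NCCN and the SAP cites NCCN directly, which PD rule governs also needs settling.

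**What to change.** 1. In Appendix 4, widen the PET condition for extramedullary PD so that PET positivity at one or more earlier sites *or in the new mass* satisfies it.
2. State that an assessment meeting PD, including the amended PET condition, is not scored CR or PR at that assessment. Worded this way, a PET-negative residual mass with no new lesion remains CR.
3. Have SAP Section 6 name Appendix 4 as the governing extramedullary criteria, and add PD to the list of exceptions to NCCN at the start of Appendix 4.

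The cost is a few sentences. No new data are needed, because the assessments are already planned for listing by subject. SAP Section 1 allows changes after finalization to be documented in the study report. The downside is that a response rate may become slightly lower.

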Appendix 5.Pregnancy Precautions, Definition for Female of Childbearing
Potential, and Contraceptive Requirements

1) Definitions

a. Definition of Childbearing Potential

For the purposes of this study, a female born subject is considered of childbearing potential following the initiation of puberty (Tanner stage 2) until becoming post-menopausal, unless permanently sterile or with medically documented ovarian failure. Women are considered to be in a postmenopausal state when they are \geq 54 years of age with cessation of previously occurring menses for \geq 12 months without an alternative cause. In addition, women of any age with amenorrhea of \geq 12 months may also be considered postmenopausal if their follicle stimulating hormone (FSH) level is in the postmenopausal range and they are not using hormonal contraception or hormonal replacement therapy. Permanent sterilization includes hysterectomy, bilateral oophorectomy, or bilateral salpingectomy in a female subject of any age.

b. Definition of Male Fertility

For the purposes of this study, a male born subject is considered to be fertile after the initiation of puberty unless permanently sterile by bilateral orchidectomy or medical documentation.

2) Contraceptive Requirements for Female Subjects

a. Study Drug Effects on Pregnancy and Hormonal Contraception

GS-9973 is contraindicated in pregnancy as there is a strong suspicion of human teratogenicity/fetotoxicity in early pregnancy based on non-clinical data. In addition, GS-9973 has insufficient data to exclude the possibility of a clinically relevant interaction with hormonal contraception that results in reduced contraception efficacy; therefore, contraceptive steroids are not recommended as a contraceptive method either solely or as a part of a contraceptive regimen. Please refer to the latest version of the investigator's brochure for additional information.

b. Contraception Requirements for Female Subjects of Childbearing Potential

The inclusion of female subjects of childbearing potential requires the use of highly effective contraceptive measures. They must also not rely on hormone-containing contraceptives as a form of birth control during the study. They must have a negative serum pregnancy test at screening and a negative pregnancy test on the Baseline visit (lead-in). Pregnancy tests will be performed on a monthly basis thereafter. Female subjects must agree to one of the following methods to avoid pregnancy from Screening until 30 days from the last dose of GS-9973.

• Complete abstinence from intercourse of reproductive potential. Abstinence is an acceptable method of contraception only when it is in line with the subject's preferred and usual lifestyle.

Or

- Consistent and correct use of 1 of the following methods of birth control listed below.
 - Intrauterine device (IUD) with a failure rate of <1% per year
 - Tubal sterilization
 - Essure micro-insert system (provided confirmation of success 3 months after procedure)
 - Vasectomy in the male partner (provided that the partner is the sole sexual partner and had confirmation of surgical success 3 months after procedure)

Female subjects must also refrain from egg donation and in vitro fertilization during treatment and until at least 30 days from the last dose of GS-9973.

3) Contraception Requirements for Male Subjects

It is theoretically possible that a relevant systemic concentration may be achieved in a female partner from exposure of the male subject's seminal fluid. Therefore, male subjects with female partners of childbearing potential must use condoms during treatment and until 90 days from the last dose of GS-9973. Additional contraception recommendations should also be considered if the female partner is not pregnant.

Male subjects must also refrain from sperm donation during treatment and until at least 90 days from the last dose of GS-9973.

4) Unacceptable Birth Control methods

Birth control methods that are unacceptable include periodic abstinence (e.g., calendar, ovulation, symptothermal, post-ovulation methods), withdrawal (coitus interruptus), spermicides only, and lactational amenorrhea method (LAM). Female condom and male condom should not be used together.

5) Procedures to be Followed in the Event of Pregnancy

Subjects will be instructed to notify the investigator if they become pregnant at any time during the study, or if they become pregnant within 30 days from the last dose of GS-9973. Subjects who become pregnant or who suspect that they are pregnant during the study must report the information to the investigator and discontinue study drug immediately. Subjects whose partner has become pregnant or suspects she is pregnant during the study must report the information to the investigator.

Appendix 6. ECOO	G status
------------------	----------

Grade	ECOG
0	Fully active, able to carry on all pre-disease performance without restriction
1	Restricted in physically strenuous activity but ambulatory and able to carry out work of a light or sedentary nature, e.g., light house work, office work
2	Ambulatory and capable of all selfcare but unable to carry out any work activities. Up and about more than 50% of waking hours
3	Capable of only limited selfcare, confined to bed or chair more than 50% of waking hours
4	Completely disabled. Cannot carry on any selfcare. Totally confined to bed or chair
5	Dead

{Oken 1982}

Appendix 7.NCCN Guidelines (version 2.2016)

Response assessment

Response Criteria for Blood and Bone Marrow:

- Complete Response (CR):
 - No circulating blasts or extramedullary disease
 - No Lymphadenopathy, splenomegaly, skin/gum infiltration/testicular mass/CNS involvement
 - ➤ Trilineage hematopoiesis (TLH) and <5% blasts
 - ➤ Absolute neutrophil count (ANC) >1000/microL
 - Platelets >100,000/micro/L
 - ➢ No recurrence for 4 weeks
- Complete Response with incomplete blood count recovery (CRi):
 Meets all criteria for CR except platelet count and/or ANC
- Overall response rate (ORR = CR + CRi)
- Refractory disease
 - ➢ Failure to achieve CR at the end of induction
- Progressive disease (PD)
 - Increase of at least 25% in the absolute number of circulating or bone marrow blasts or development of extramedullary disease
- Relapsed disease
 - Reappearance of blasts in the blood or bone marrow (>5%) or in any extramedullary site after a CR

Response Criteria for Mediastinal Disease

- CT of chest with IV contrast and PET imaging should be performed to assess response
- CR: Complete resolution of mediastinal enlargement by CT. For patients with a previous positive PET scan, a post-treatment residual mass of any size is considered a CR as long as it is PET negative
- PR: >50% decrease in the sum of the product of the greatest perpendicular diameters (SPD) of the mediastinal enlargement. For patients with a previous positive PET scan, post-treatment PET must be positive in at least one previously involved site
- PD: >25% increase in the SPD of the mediastinal enlargement. For patients with a previous positive PET scan, post-treatment PET must be positive in at least one previously involved site
- No Response (NR): failure to qualify for PR or PD
- Relapse: recurrence of mediastinal enlargement after achieving CR. For patients with a previous positive PET scan, post-treatment PET must be positive in at least one previously involved site

SAE	serious adverse event
SAP	statistical analysis plan
SE	standard error
SOC	system organ class
SOP	standard operating procedure
StD	standard deviation
Syk	Spleen tyrosine kinase
TEAE	treatment emergent adverse event
TFL	tables, figures and listings
uL	microliter
ULN	upper limit of the normal range
US	United States
VCR	vincristine
WHO	World Health Organization

1. INTRODUCTION

This statistical analysis plan (SAP) describes the statistical analysis methods and data presentations to be used in tables, figures, and listings (TFLs) in the clinical study report (CSR) for Study GS-US-339-1560. This SAP is based on the study protocol GS-US-339-1560 Amendment 5 dated 13 April 2018 and the electronic case report form (eCRF). The SAP will be finalized before database finalization. Any changes made after the finalization of the SAP will be documented in the CSR.

The study was originally designed to evaluate the safety, efficacy, tolerability, and pharmacokinetics (PK) of entospletinib (ENTO) in combination with vincristine (VCR) and dexamethasone in 2 stages: (1) Phase 1b dose-escalation; (2) Phase 2 expansion for relapsed or refractory Acute Lymphoblastic Leukemia (ALL). However, due to the low response rate to ENTO in combination with VCR and dexamethasone in Phase 1b portion, the Sponsor has decided to not proceed with the Phase 2 portion of this study. Subjects currently on study will continue to be treated and/or followed until the end of study criteria are met. A synoptic CSR will be generated, and this SAP describes the analyses for Phase 1b only.

